6.1.1 Adverse Event Term

An adverse event term is determined by the investigator/site coordinator, based on the patient’s symptom or condition, and is described on the form. Potential adverse events may include, but are not limited to, the following:

- Implant breakage;
- Component disarticulation;
- Component degradation;
- Implant displacement/dislocation;

- Pedicle disruption/failure;
- Allergic reaction to implant materials;
- Reaction to implant wear debris;Fracture/damage to pedicle;
- Fracture/damage to spinous process;
- Failure of bone to heal around implant;
- Bone resorption;
- Non-union, delayed union;
- Bursitis;
- Vessel damage/bleeding;
- Nausea and/or vomiting;
- Superficial infection;
- Deep wound infection;
- Hematoma at surgical site;
- Incisional pain;
- Pulmonary embolism;
- Stroke;
- Myocardial infarction;
- Coronary episode;
- Pneumonia;
- Kidney failure;
- Bowel obstruction
- Dural tear;
- Thrombosis;
- Nerve injury;
- Neuropathy
- Cauda equina syndrome;
- Transverse process fracture;
- Pseudomeningocele;
- Paralysis;
- Spinal fluid leakage;
- Spinal cord damage;
- Bone fracture;
- Spinous process fracture;
- Spondylosis;
- Heterotopic bone formation;
- Scoliosis;
- Kyphosis;
- Segmental instability;
- Decrease in neurological function;
- Worsening leg and/or back pain;
- Worsening pain associated with stenosis;
- Degeneration at adjacent level(s);

- Respiratory distress;
- Wound dehiscence;
- Wound swelling;
- Death

6.1.2 Relationship to Procedure

The relationship between an adverse event and the surgical procedure (investigational or control treatment) will be assessed on the basis of the following definitions:

- **Definitely Related:** Clear-cut temporal association and no other possible cause.
- **Probably Related:** Clear-cut temporal association and a potential alternative etiology that is not apparent.
- **Possibly Related:** Temporal association is less clear and other etiologies are also possible.
- **Probably Not Related:** Temporal association and the nature of the event is such that the surgical procedure is not likely to have had any association with the observed event (cause and effect relationship improbable but not impossible)
- **Definitely Not Related:** There is no temporal association and/or evidence exists that the event is definitely related to another etiology

6.1.3 Relationship to Device

The relationship between an adverse event and the implanted device (investigational or control) will be assessed on the basis of the following definitions:

- **Definitely Related:** Clear-cut temporal association and no other possible cause.
- **Probably Related:** Clear-cut temporal association and a potential alternative etiology that is not apparent.
- **Possibly Related:** Temporal association is less clear and other etiologies are also possible.
- **Probably Not Related:** Temporal association and the nature of the event is such that the device is not likely to have had any association with the observed event (cause and effect relationship improbable but not impossible)
- **Definitely Not Related:** There is no temporal association and/or evidence exists that the event is definitely related to another etiology

6.1.4 Severity

The severity of an adverse event will be assessed according to the World Health Organization (WHO) Recommendations for Grading of Acute and Subacute Toxic Effects. The following definitions are used:

- **Mild (Grade 1):** The adverse event is noticeable to the patient but does not interfere with routine activity. The adverse event does not require implant removal.
- **Moderate (Grade 2):** The adverse event interferes with routine activity but responds to symptomatic therapy or rest. The adverse event does not require implant removal.
- **Severe (Grade 3):** The adverse event significantly limits the patient's ability to perform routine activities despite symptomatic therapy. In addition, the adverse event may require removal of the implant.
- **Life-threatening (Grade 4):** The adverse event may require removal of the implant. The patient is at immediate risk of death.

6.1.5 Action Taken

Adverse events or treatment failures may lead to further actions as required to resolve the adverse event. The following actions will be identified for each adverse event:

- **None:** No further actions taken to resolve adverse event
- **Medication:** Medications are prescribed to treat the adverse event
- **Index Level Surgery:** A procedure at the original involved level in which all or part of the original implant configuration is modified or removed, with or without replacement, or additional surgical instrumentation is implanted. This includes decompression, surgical repair of a dural tear, wound debridement, irrigation and drainage at the original level. (Details are submitted on a Surgical Intervention Form SA11.)
- **Other:** Any additional procedure that is not one of the above categories

An index level surgery that is a revision, removal, reoperation, or supplemental fixation will be classified as a treatment "failure". Other index level surgery, such as debridement, irrigation and drainage, and repair of a dural tear, will not be classified as a treatment "failure". All patients having secondary surgical procedures will be followed for the duration of the study for safety, in accordance with Section 5.6.

6.1.6 Outcome

The outcome of each adverse event will be identified as one of the following categories:

- **Resolved:** The adverse event has been resolved and is no longer continuing
- **Temporary Disability:** Disability that is short term and is not considered a permanent disability
- **Permanent Disability:** Disability that has been determined to be permanent and not temporary
- **Death:** Death of the patient due to the adverse event

6.2 Serious Adverse Events

Serious adverse events (SAEs) are defined as adverse events that are life-threatening, or ones that result in permanent impairment of a body function or permanent damage to a body structure, or they necessitate medical or surgical intervention to preclude permanent impairment of a body function or permanent damage to a body structure.

An SAE is any untoward medical occurrence that:

- Results in death,
- Is life-threatening,
- Requires inpatient hospitalization or prolongation of existing hospitalization,
- Results in persistent or significant disability/incapacity, or
- Is a congenital anomaly/birth defect.

Any Serious Adverse Event must be reported to Globus Medical, Inc. by the investigator within 24 hours of first learning about the event. An Adverse Event Case Report Form must be sent to Globus Medical within ten working days of knowledge of the event to the fax number listed on the case report form. The event is documented on the Adverse Event Case Report Form, with SAE denoted on the form. Participating Institutional Review Boards will be notified in accordance with their respective procedures.

6.3 Unanticipated Adverse Device Effects

An Unanticipated Adverse Device Effect (UADE) is defined as any serious adverse effect on health or safety or any life threatening problem or death caused by or associated with the device if that effect, problem or death **was not previously identified in nature, severity or degree of incidence in the investigational plan**, or any other unanticipated serious problem associated with the device that relates to the rights, safety or welfare of subjects.

Any unanticipated adverse device effects must be reported to Globus Medical, Inc. within 24 hours of first learning about the event. A written report must be made to Globus Medical, Inc. within ten working days of knowledge of the event to the fax number listed

on the case report form. The event is documented on the Adverse Event Case Report Form, with UADE denoted on the form. The Institutional Review Board must also be notified within ten working days or sooner depending on their requirements.

Globus Medical, Inc. will also notify the appropriate regulatory agencies, and all participating investigators and Institutional Review Boards in writing within ten working days after learning of any unanticipated adverse device effects.

[figure not shown]
6.4 Patient Death

Patient death during the investigation must be reported by fax to Globus Medical, Inc. within 24 hours of the Investigator's knowledge of the death. Notification of death must include a brief statement of the relevant details and be signed by the Investigator or Co-Investigator. A copy of the death records, death certificate and an autopsy report (if performed) must be sent to Globus Medical, Inc.

6.5 Subsequent Surgical Interventions

All additional surgeries are to be reported, and are reported according to Section 6.1.5 Action Taken. Details are reported on the Surgical Intervention Form (SA11). Surgical procedures subsequent to the original surgery will be categorized as follows:

- A revision is a procedure that adjusts or in any way modifies or removes *part* the original implant configuration with or without replacement of a component, and may also include adjusting the position of the original configuration.
- A removal is a procedure where *all* of the original implant configuration is removed with or without replacement.
- A reoperation is any surgical procedure at the involved level that does not require removal, modification, or addition of any components of the system (excluding surgical repair of a dural tear, irrigation and drainage, or wound debridement).
- A supplemental fixation is a procedure in which additional instrumentation not under study in the protocol is implanted at the involved level.

If an adverse tissue reaction is suspected before or during revision, report specific observations (operative site and device), any histological data (biopsy), MRI/CT, and metal allergy data on SA11, in addition to the operative report and chart notes.

[REDACTED]

[REDACTED]

[REDACTED]

[REDACTED]

[REDACTED]

[REDACTED]

[REDACTED]

[REDACTED]

[REDACTED]

8.0 STATISTICAL ANALYSIS PLAN

8.1 Analysis Populations

Primary Analysis Population:

The principal analysis of the primary and secondary endpoints will utilize the intent-to-treat (ITT) patient population. The ITT population will include all randomized subjects for whom surgery is attempted. Subjects for whom surgery is attempted but not successfully completed will be considered treatment failures. Randomized subjects in whom surgery is not attempted will be described in detail in a separate section of the study report.

Secondary Analysis Populations:

The primary and secondary objectives will be further analyzed using an as-treated (AT) analysis performed on all randomized subjects according to the treatment actually received.

The primary and secondary objectives will be further analyzed using a per protocol (PP) analysis performed on an evaluable patient population. The evaluable population will consist of all ITT subjects that: [1] meet critical study eligibility criteria and have no significant protocol deviations based on Clinical Events Committee assessment; [2] have the assigned procedure completed; and [3] completed the 24-month follow-up assessment.

Training Population:

This patient population will include all non-randomized AFRS treated patients enrolled during the pivotal phase of the trial as training cases at the site. A maximum of two patients per site for a total of 60 patients will be included in this cohort. Training cases will be described separately from randomized patients in the final study report and will be presented primarily using descriptive statistics. This patient population will be used to understand the learning curve in the use of the device by assessing the results of the Training cases relative to those obtained in the Treatment group arm of the randomized study.

An additional presentation of the safety data in which all of the patients treated with the AFRS device (non-randomized and randomized) are combined as one cohort and compared to the control group will be included.

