3.0 STUDY DESIGN AND METHODOLOGY

3.1 Study Design

The pivotal evaluation of the AFRS investigational device will incorporate a multi-center, prospective, randomized, and concurrently controlled study design. Up to 30 sites will enroll and treat a minimum of 300 patients and a maximum of 750 patients into the study. In addition, up to 60 training cases (two per clinical site) may be completed by participating investigators, at the discretion of the Sponsor and participating site clinicians.

The investigational group will consist of at least 200 patients who receive the AFRS device. The control group will consist of at least 100 patients who will receive an instrumented posterolateral fusion. This number is based upon the sample size required to provide reasonable assurance of safety and effectiveness using the concurrent control and allowing for 15 percent loss to follow-up. The patients will be allocated to treatment assignment using a 2:1 randomization scheme.

The outcome measures in this study will include the following: the SF-36 questionnaire, the ZCQ, the ODI, a neurological assessment, a symptomatic pain assessment, as measured with the VAS Index, a patient satisfaction questionnaire, and an independent radiological assessment. In addition, outcome measures will be included to support potential reimbursement with healthcare providers. Patients in both treatment groups will be followed for 24 months postoperatively.

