
5.6 Patient Follow-Up

Patient follow-up will be completed postoperatively; at hospital discharge, at 6 weeks and 3, 6, 12, and 24 months as outlined in the Assessment Schedule located in **Appendix 1**. After 24 months, patients will be evaluated annually, as required by FDA. The study assessments required at each follow-up visit are detailed below.

All questionnaires related to patient outcome will be completed at each visit independently by the patient prior to any clinical evaluations and will be administered by study personnel who are not healthcare providers directly associated with the study.

Patients who undergo removal, revision, or reoperation of, or supplemental fixation to, the investigational or control device will continue to be followed for safety and effectiveness outcome data.

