5.7 Patient Discontinuation

All patients enrolled into the current study and who have undergone one of the study treatments, will be followed for 24 months postoperative and until all FDA requirements are met, potentially up to 10 years postoperative. Acceptable reasons for not evaluating a patient through the follow-up period include:

- a) Patient Lost to Follow-Up: Unable to locate patient despite documented attempts to notify the patient via telephone and by certified mail. A patient will not be considered lost to follow-up until the last scheduled follow-up visit (24 month study time point).
- b) Patient Request to Terminate: The patient requests to terminate his/her involvement in the study, therefore withdrawing his/her consent to participate in the study (the investigator must thoroughly document the reasons for termination).
- c) Patient Death: If possible, an autopsy and/or death certificate should be obtained in order to document the cause of death.

If a patient discontinues from the study (regardless of the reason), the investigator will record the reason for withdrawal on the appropriate CRFs. Every effort shall be made to have discontinued patients (as appropriate) return for an “Early Termination Visit” to collect the required safety evaluations as detailed in the protocol.

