8.4 Predictions

Predicted values of 2-year outcomes for those subjects who have not reached 2 years will be based on the intermediate outcomes measured at 6 months and 12 months. 3 month data will not be used in any of the predictive modeling. During this time, patients are continuing the post-operative healing process and may not be appropriate for this purpose.

At the time point of an interim analysis, there will be 4 types of subjects: subjects with complete 2-year data; subjects with 1-year data but no 2-year data; subjects with 6-month data but no 1-year or 2-year data, and subjects who have begun the study but do not yet have 6-month or 1-year data. For those with 6-month or 1-year interim data but no 2-year data, subjects will be considered to be one of the following:

- a) successes (i.e., meet all the criteria to be treatment successes, except that this is measured at 6 months or 1 year rather than 2 years)
- b) recoverable non-successes (i.e., do not meet the criteria to be successes, but it is still possible that they might become successes at 2 years)
- c) failures (i.e., subjects who cannot meet the definition of success at 2 years because of an event such as a device removal or re-operation.)

Subjects without 2-year follow-up data will thus be considered to be in one of 14 states (7 for each treatment group). The 7 states are:

- no interim data
- success at 6 months
- recoverable non-success at 6 months
- failure at 6 months
- success at 1 year
- recoverable non-success at 1 year
- failure at 1 year

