Interim failures can be imputed to be failures at 2 years, with certainty. For each of the remaining 10 states (5 for each treatment group), the probability of becoming a success at 2 years is modeled via a Beta (a,b) prior distribution which is updated to a Beta($a+S$, $b+F$) distribution, based on the number S and F of subjects who went on from that state to become 2-year successes and failures, respectively. For example, if, in the treatment group at an interim analysis time point, 70 of 100 subjects with 2-year data are successes, and if 50 of the 70 two-year successes also met the definition of success at 1 year, then the transition probability from the 1-year success state to the 2-year success state will be modeled as Beta ($a+50$, $b+20$). At an interim analysis time point, any treatment-group subjects residing in the success-at-1-year-but-without-2-year-data state will have their 2-year outcome predicted on the basis of this Beta($a+50$, $b+20$) distribution. **Figure 8.4.1** graphically depicts the various transitions for a generic treatment group (treatment or control). The numerical example above would apply to transition #2 in the figure.

[figure not shown]
[figure not shown]

Figure 8.4.1. Graphical depiction of transitions from interim states (S = Success, R = Recoverable Non-Success, No Data) to 2-year Success. Each transition is assigned a Beta (a,b) prior distribution which is updated as data are gathered.

Prior Distributions for Transition Probabilities

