By varying γ , we can examine the impact of a biasing influence on the study results. The values $\gamma = -\infty$ and $\gamma = +\infty$ correspond to setting all such observations to be failures or successes, respectively. The impact of various values of γ will be examined and presented in a sensitivity analysis, representing both positive and negative biases for the two groups.

[REDACTED]

[REDACTED]

[REDACTED]

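### Per-protocol criterion [3] shows no exception for patients already certain to be 2-year failures, so per-protocol success rates read too high if those patients miss the 24-month visit more often than others

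*Combined protocol and SAP*

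**What the plan says.** Section 8.1 makes ITT the principal analysis population and adds a per-protocol analysis of the primary and secondary objectives. The evaluable set has three conditions. The first is eligibility without significant deviations. The other two are that subjects "have the assigned procedure completed; and [3] completed the 24-month follow-up assessment". No exception to [3] is visible.

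Section 8.4 defines interim failures as "subjects who cannot meet the definition of success at 2 years because of an event such as a device removal or re-operation", and then says: "Interim failures can be imputed to be failures at 2 years, with certainty". Section 8.6 repeats that rule for missing data.

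Three places keep such patients under observation:
- Section 5.6: patients with a removal, revision, reoperation or supplemental fixation "will continue to be followed for safety and effectiveness outcome data".
- Section 6.1.5: "All patients having secondary surgical procedures will be followed for the duration of the study for safety".
- Section 5.7: treated patients "will be followed for 24 months postoperative and until all FDA requirements are met".

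Section 5.7 nevertheless accepts loss to follow-up, withdrawal and death as reasons for no evaluation, and describes the early termination visit as collecting safety evaluations. Section 4.0 releases patients who withdraw consent after treatment from further visits, while still counting them in the cohort. Section 3.1 bases the minimum numbers on the size needed "using the concurrent control and allowing for 15 percent loss to follow-up".

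**The concern.** For a known failure the 24-month visit adds nothing to the primary outcome: the plan already treats that outcome as certain. Criterion [3] still removes the patient if the visit is missed. The ITT analysis counts that failure and the per-protocol analysis deletes it.

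The per-protocol analysis is a planned second look at the non-inferiority objective, and readers will set it beside ITT. If known failures return less often than others, each arm's per-protocol success rate is inflated. The AFRS-minus-control difference then moves in favour of whichever arm loses more of its known failures. Agreement between the two analyses would be somewhat less informative than it looks.

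**Working it through.** **Figures in the documents.** The plan gives no figure for the per-protocol analysis, so there is none to reproduce. Usable figures are the 2:1 allocation and minimum N of 300 (200 and 100), the 15% loss allowance (section 3.1) and the 0.15 margin at the win analyses (section 8.3). Failure, success and return rates are not visible, so those below are assumptions.

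**Formulas.** Per arm, let S be true success, T terminal (known) failure, NS = 1 − S − T, w non-return among all others, and wt non-return among known failures.
- Per-protocol rate as written: S(1−w) / [(S+NS)(1−w) + T(1−wt)].
- Loss per arm: (1−T)w + T·wt. Overall loss: (2 × AFRS + control)/3.

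**Base case.** AFRS T = 0.15, S = 0.65; control T = 0.08, S = 0.72; true difference −7.0 points; w = 0.10. At wt = 0.50:
- AFRS: 0.65×0.90 / (0.85×0.90 + 0.15×0.50) = 0.585/0.840 = 0.696.
- Control: 0.72×0.90 / (0.92×0.90 + 0.08×0.50) = 0.648/0.868 = 0.747.
- Loss: 0.085 + 0.075 = 16.0% and 0.092 + 0.040 = 13.2%; overall (32.0 + 13.2)/3 = 15.1%.

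| w | wt | AFRS | Control | Difference (points) | Shift (points) | Overall loss |
|---|---|---|---|---|---|---|
| 0.10 | 0.10 | 0.650 | 0.720 | −7.0 | 0 | 10.0% |
| 0.10 | 0.30 | 0.672 | 0.733 | −6.1 | +0.9 | 12.5% |
| 0.10 | 0.50 | 0.696 | 0.747 | −5.0 | +2.0 | 15.1% |
| 0.05 | 0.30 | 0.677 | 0.735 | −5.9 | +1.1 | 8.2% |
| 0.05 | 0.50 | 0.700 | 0.748 | −4.9 | +2.1 | 10.7% |

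With w = 0.10 the allowance is reached at wt = 0.495, where the shift is +1.96. At N = 300, wt of 0.30 or 0.50 deletes 200×0.15×wt = 9 or 15 AFRS known failures and 100×0.08×wt = about 2 or 4 control known failures.

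**Direction.** With the arms' failure and success rates swapped and w = 0.10, the shifts are −0.9 and −2.0, against AFRS. With T = 0.10 and S = 0.70 in both arms, both rates read 0.716 or 0.733 and the difference stays 0. If known failures return more often than others, the sign within an arm reverses: with S = 0.70, T = 0.10, 85% overall completion and all known failures returning, the rate is 0.70×0.833 / (0.90×0.833 + 0.10) = 0.686, or −1.4 points.

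**Two points is not a ceiling.** With w = 0.05 the overall loss is (0.131 + 0.38·wt)/3, which reaches 15% at wt = 0.84. There AFRS reads 0.6175/0.8315 = 0.743 and control 0.684/0.8868 = 0.771. The difference is −2.9 points, a shift of about +4.

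**Check on the repair.** Keeping every known failure while still dropping other non-completers gives S(1−w) / [(S+NS)(1−w) + T]. With w = 0.10 this is 0.585/0.915 = 0.639 and 0.648/0.908 = 0.714, a difference of −7.4, so it errs the other way. Predicting the other non-completers as well gives [S/(S+NS)] × (S+NS) = S, that is 0.650 and 0.720, if their non-return is random within state.

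**The case against.** The strongest case against is that the matter is settled where it counts. ITT is principal and takes interim failures as failures. Section 8.6 adds a shift analysis whose range of values "will be examined and presented in a sensitivity analysis, representing both positive and negative biases for the two groups", including all such missing outcomes set to failure. No visible win rule uses the per-protocol set. All of this stands and confines the point to one secondary analysis.

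Nor is the premise of lower return shown. Sections 5.6, 5.7 and 6.1.5 keep reoperated patients in follow-up, and every return rate above is assumed. That also stands. Those provisions reduce non-return, but they do not put a patient who misses the visit back into the set.

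The shift is small beside sampling error. Assuming 0.70 success and 15% loss at N = 300 (170 and 85 completers), the standard error is √[0.21(1/170 + 1/85)] = 6.1 points, so 0.9 to 2.0 points is about 0.15 to 0.33 of it. This supports a low grade, not dismissal.

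A completers-only per-protocol set is also a conventional choice, and adding predictions brings it closer to ITT. That is a fair reason to keep the completers-only result and report both.

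Redacted text follows sections 3.5.1 and 8.6 and falls within 8.2 and 8.3, and section 8.8 is not visible. An exception could sit there; if so, the sponsor need only point to it.

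A reader might infer that the non-inferiority conclusion is biased, or that the rule favours AFRS. The documents support neither: the principal analysis does not use criterion [3], and the sign of any between-arm effect depends on unknown rates.

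**Conclusion.** The concern holds as a minor, conditional point about a stated rule. Followed exactly, criterion [3] deletes known failures who miss the 24-month visit. This raises each arm's per-protocol success rate if they return less often than others, and does nothing if return is equal.

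Under the assumed rates, the listed between-arm shifts run from 0 to about 2 points in size up to roughly the 15% allowance. About 4 points is possible within the allowance under the extreme assumption of 84% non-return among known failures and 5% among others. All are well inside the 15-point margin. Confidence is medium, because the return rates are unknown and part of the plan is blacked out.

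**What to change.** For the primary endpoint, reword criterion [3] along these lines: *24-month assessment completed, or classified before that visit as a failure in the section 8.4 sense*. Use the same failure list as the primary analysis. State that it covers events at any time before the 24-month visit, because the interim states listed in section 8.4 stop at 1 year.

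Because that clause alone over-represents failures, also predict the remaining non-completers who meet [1] and [2] with the section 8.4 model, using the flat priors already set for win looks. Report this next to the completers-only per-protocol result. Tabulate per-protocol exclusions by arm and reason, with known failures identified.

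The cost is one clause, one more run of an existing model and one table, with no new data. The downsides to state are:
- per-protocol rates may be slightly less favourable;
- the predicted version relies on the section 8.4 model;
- the per-protocol denominators for the primary and secondary objectives will differ.

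Separately, sections 5.4 and 5.6.7 class index-level denervation before the 24-month visit as a study failure, while the visible success definition in section 3.5.1 does not mention it. These sections must be reconciled so that the failure list is unambiguous.
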